6.2.5.3 Medical History

Medical history is tabulated by system organ class (SOC) and PT, and displayed in descending order of overall frequency within SOC and PT.

6.2.5.4 Prior Non-study Medications

The following non-study medications are tabulated by therapeutic class and preferred name:

- Prior medications: all; prophylactic migraine
- Current medications: all; prophylactic migraine
- Stable prophylactic migraine medications through randomization.

Medications are displayed in descending order of overall frequency within therapeutic class and preferred name. See Section 6.2.6.2.

Stable medications through randomization are defined as those taken > 3 months before informed consent and through randomization, i.e., (1) informed consent date – imputed medication start date > 90 days, and (2) IWRS randomization date ≤ imputed medication stop date.

6.2.6 Exposure

6.2.6.1 Study Therapy

Subjects report study drug exposure in the eDiary, whereas sites report study drug accountability on the Drug Accountability CRF.

eDiary study drug exposure is tabulated by as-randomized treatment group and overall for the full analysis set that includes the number and percentage of subjects in the following categories:

- Study drug taken (i.e., study drug start date/time not missing)
 - Study drug taken before using eDiary (see Section 7.5.1.1)
 - Study drug actually received different from randomized treatment assignment (i.e., as-treated treatment group not equal to as-randomized treatment group).
- Study drug not taken (i.e., study drug start date/time missing).

Study drug accountability is tabulated by as-randomized treatment group and overall for the full analysis set, and includes the number and percentage of subjects in the following categories:

- Kit dispensed
- Kit not dispensed
- Kit dispense not reported (i.e., missing)
- Kit dispensed and returned
 - Investigational product (IP) used
 - IP not used
 - IP use not reported (i.e., missing)
- Kit dispensed and not returned
- Kit dispensed and return not reported (i.e., missing).

Two 2 × 3 cross-tabulations of eDiary study drug exposure and study drug accountability are provided for the full analysis set by overall treatment group only. The number and percentage of subjects in each category are tabulated follows:

- Categories for study drug exposure in rows are “study drug taken” and “study drug not taken”. Categories for study drug accountability in columns are “kit dispensed and returned”, “kit dispensed and not returned/return not reported”, and “kit not dispensed/dispense not reported”.

- Categories for study drug exposure in rows are “study drug taken” and “study drug not taken”. Categories for study drug accountability in columns are “IP used”, “IP not used”, and “IP use not reported”.

A by-subject listing of eDiary study drug exposure and study drug accountability is provided for the full analysis set containing the following:

- eDiary: study drug date/time. Only eDiary records with non-missing study drug date/time are displayed.
- Drug accountability: kit dispensed status (yes, no), kit returned status (yes, no), kit dispensed date, kit returned date, kit ID, IP used status (IP used, IP not used).

The listing identifies the following: invalid kit IDs; subjects who took study drug, had a kit dispensed, but did not return a kit or had kit return status missing as per first cross-tabulation; and subjects with discrepant data as per second cross-tabulation, i.e., (1) eDiary study drug date/time is non-missing but IP not used or not reported, or (2) eDiary study drug date/time is missing but IP used.

An administrative listing of IP batch numbers is provided for the safety analysis set. Refer to the Zavegepant Core SAP for listing contents.

6.2.6.2 *Concomitant Non-study Medications*

The following non-study medications are tabulated by therapeutic class and preferred name and by as-treated treatment group for the safety analysis set:

- Concomitant medications: all; prophylactic migraine
- Rescue medications.

Concomitant and rescue medications are displayed in descending order of zavegepant frequency within therapeutic class and preferred name. Imputed medication start and stop dates are used to assign non-study medication type (previous, current, concomitant, or follow-up) to all non-study medications except rescue medications. Refer to the Zavegepant Core SAP for definitions of non-study medication types, non-study medication counting rules in frequency tables, and non-study medication start and stop date imputation.

Rescue medications are also tabulated by as-randomized treatment group for the efficacy analysis set to support efficacy.

A by-subject listing of non-study medications is provided by therapeutic class and preferred name for the enrolled analysis set. Medication types are identified. Prophylactic migraine and rescue medications are identified. Refer to the Zavegepant Core SAP for listing contents.

A by-subject listing of rescue medications is provided by therapeutic class and preferred name for the safety analysis set. The listing also displays the number of hours that rescue medication is taken from study drug.

Both listings display treatment day derived from the imputed start date and COVID-19 visit impact code for visits impacted by COVID-19 (see Section 9.1.5.2).

The following conventions apply to non-study medications:

- Non-study medications are identified from those reported on the Concomitant Medication and Rescue Medication CRFs. Note that the Concomitant Medication CRF links medical history and AE terms respectively to the Medical History and AE CRFs using numeric variables.
- Migraine standard of care medications are defined as either acute migraine or prophylactic migraine medications from the indication panel of the CRF.
- Concomitant medications are defined as those taken on or after study drug, i.e., (1) study drug start date \leq imputed start or stop date, or (2) rescue medications.
- Rescue medications are defined as non-study medications reported on the Rescue Medication CRF with complete medication dates, and either (1) medication date/time after the study drug start date/time if the medication time and study drug start time are both not missing, or (2) medication date at or after study drug start date if the medication time or study drug start time is missing. Rescue medication dates are not imputed. Rescue medication times are not imputed, unless specified otherwise (see Section 6.3.4.3).

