The intercurrent event of rescue medication use is handled using Rescue Medication = Failure (RM=F), i.e., subjects who take rescue medication are classified as failures for all efficacy assessments that are reported at or after taking rescue medication, i.e., (1) rescue medication start date/time \leq eDiary finding date/time if start time is not missing, or (2) rescue medication start date \leq eDiary finding date if start time is missing; see Sections 6.2.6.2 and 7.1). This method applies to all efficacy analyses, except the secondary endpoint of rescue medication use within 24 hours postdose.

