6.3.2 *Primary Efficacy Endpoints*

Both co-primary efficacy endpoints are evaluated for the efficacy analysis set.

A by-subject listing of pain freedom and MBS freedom outcomes at each postdose time point is provided for the randomized analysis set that includes prophylactic migraine medication use at randomization, rescue medication start date/time (see Section 7.1), time to rescue medication start date/time in hours (see Section 6.3.3.8), pain intensity at the time of dosing, MBS on study before dosing, and reason for exclusion from the efficacy analysis set (see Section 6.2.1). See Section 6.3.4.1 for efficacy outcomes.

6.3.2.1 *Pain Freedom at 2 Hours Postdose*

Pain freedom at a single time point postdose is defined as having a pain intensity of none at that time point.

For the co-primary endpoint, subjects who meet both of the following criteria are classified as responders:

- Pain intensity of none at 2 hours postdose, i.e., in the 2-hour postdose analysis window
- No rescue medication taken at or before 2 hours postdose, i.e., (1) rescue medication start date/time missing, or (2) rescue medication start date/time > {eDiary finding date/time for the pain intensity assessment in the 2-hour postdose analysis window}.

Subjects who have any of the following are classified as failures:

- Rescue medication taken at or before 2-hours postdose (RM=F), i.e., (1) rescue medication start date/time \leq {eDiary finding date/time for the pain intensity assessment in the 2-hour postdose analysis window}, or (2) (rescue medication start date/time – study drug start date/time) \leq 135 minutes, the upper bound of the 2-hour postdose analysis window (see Section 7.3), if pain intensity is missing in the 2-hour postdose analysis window.
- Mild, moderate, or severe pain intensity at 2 hours postdose, i.e., in the 2-hour postdose analysis window
- Missing pain intensity at 2 hours postdose (NC=F), i.e., in the 2-hour postdose analysis window.

Main Analyses

Pain freedom outcomes at 2 hours postdose are tabulated by treatment group (see Section 6.3.4.1). Outcomes are tabulated analogously for each subgroup level of all efficacy subgroups of interest specified in Section 4.3.

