Treatment group comparisons of the percentage of subjects with sustained pain freedom from 2 to 48 hours postdose use analogous methods as the main analysis of the co-primary endpoint of pain freedom with NC=F, NC1=F, and RM=F (see Section 6.3.2.1).

6.3.3.7 *Freedom from Photophobia, Phonophobia or Nausea at 2 Hours Postdose*

Freedom from each symptom (nausea, phonophobia, photophobia) at 2 hours postdose is assessed separately. Symptom status is measured as present or absent for each symptom (nausea, phonophobia, photophobia).

Symptom freedom at a single time point postdose is defined as a symptom absent at that time point for subjects with the symptom present at the time of dosing. Thus, all analyses of symptom freedom are based on the efficacy analysis set with the symptom present at the time of dosing (see Section 7.5.2), e.g., nausea freedom at a single time point postdose are based on subjects with nausea present at the time of dosing.

Symptom freedom outcomes at 2 hours postdose are tabulated by treatment group (see Section 6.3.4.1).

Treatment group comparisons of the percentage of subjects with symptom freedom at 2 hours postdose use analogous methods as the main analysis of the co-primary endpoint of pain freedom with NC=F and RM=F (see Section 6.3.2.1).

6.3.3.8 *Rescue Medication Use within 24 Hours Postdose*

Analyses are based on the evaluable efficacy analysis set, i.e., subjects in the efficacy analysis set with rescue medication start date on or before study drug start date + 1 day and missing rescue medication start time are excluded. Time to rescue medication use is measured from the study drug start date/time to the rescue medication start date/time.

No analysis window around the 24-hour postdose time point is used.

Rescue Medication Use within 24 Hours Postdose

Rescue medication use within 24 hours postdose is defined as time to rescue medication use ≤ 24 hours.

Treatment group comparisons of the percentage of subjects using rescue medication within 24 hours postdose use analogous methods as the main analysis of the co-primary endpoint of pain freedom, except that the NC=F and RM=F methods are not applied because they are not applicable to this endpoint (see Section 6.3.2.1).

Time to Rescue Medication Use through 24 Hours Postdose

Time to rescue medication use through 24 hours postdose is assessed by treatment group as follows:

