7 CONVENTIONS

7.1 Derived Dates

Derived dates are defined as follows:

- Study drug start date/time: Earliest (1) study medication dose date and time from the eDiary Migraine Report, or (2) study medication intake date and time from the Study Medication Intake Report (see Section 7.5.1). This date is used to define analysis periods.
- Rescue medication start date/time: Earliest rescue medication date/time (see Section 6.2.6.2). Missing time is considered to be earlier than non-missing time on the same date.
- Imputed rescue medication start date/time: This is used only for time-to-event efficacy analyses in Section 6.3.4.3, and not for time to rescue medication use analyses in Section 6.3.3.8.
 - If the rescue medication start date and time are both not missing, then the imputed rescue medication start date/time is set to the rescue medication start date/time.
 - If the rescue medication start time is missing and the rescue medication start date is equal to the study drug start date, then the imputed rescue medication start date/time is set to the study drug start date/time.
 - Otherwise, if the rescue medication start time is missing and the rescue medication start date is equal to a postdose eDiary finding date with non-missing efficacy data, then the

imputed rescue medication start date/time is set to the first eDiary finding date/time corresponding to non-missing efficacy data.

- Otherwise, if the rescue medication start time is missing and rescue medication start date is equal to the study drug start date + 1 day, then the imputed rescue medication start date/time is set to the study drug start date/time + upper bound of the X -hour analysis window (see Table 5).
- COVID-19 visit date: (1) Complete visit date, if it exists; (2) otherwise, complete date the visit was planned to occur for a missed visit (see Section 9.1.1).
- Last contact date: (1) Earliest complete death date from AE CRFs, if it exists; (2) otherwise, the maximum complete date of the following: AE start or stop; COVID-19 visit only for in-person or remote visits; ECG; eDiary finding; eDiary study drug start; informed consent; IWRS randomization; laboratory collection; nasal inspection; non-study medication start or stop; physical measurement; procedure; rating scale; questionnaire; vital sign; visit. If the last contact date is after the most recent raw database creation date, then it is set to the most recent raw database creation date.

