- Death date: Last contact date derived only for subjects who died (see Section 6.4.1).

No date imputations are performed on these derived dates. Complete dates are those with valid, non-missing day, month, and year.

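### A recorded rescue with an incomplete date escapes the rescue-equals-failure rule and is read as no rescue

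*SAP*

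**What the plan says.** SAP 6.2.6.2 sets the definition: "Rescue medications are defined as non-study medications reported on the Rescue Medication CRF with complete medication dates", with the further condition that the medication follows study drug. It adds: "Rescue medication dates are not imputed". SAP 7.1 explains the term: "Complete dates are those with valid, non-missing day, month, and year". The same section takes the rescue start date/time as the earliest among records that satisfy 6.2.6.2.

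The responder rule in SAP 6.3.2.1 then reads: "No rescue medication taken at or before 2 hours postdose, i.e., (1) rescue medication start date/time missing", with a start later than the 2-hour assessment as the alternative. The same treatment of a missing start appears in 6.3.2.2 (freedom from most bothersome symptom), 6.3.3.3 and 6.3.3.4 (sustained relief) and 6.3.4.1 (outcomes over time). Sustained freedom (6.3.3.5, 6.3.3.6) and relapse (6.3.3.9) inherit it by cross-reference.

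A missing time has its own rules. In 6.3 the comparison falls back to dates, setting the rescue date against the "eDiary finding date if start time is missing". In 6.3.3.8 a subject is removed from the 24-hour rescue endpoint if the rescue date is no later than the day after dosing and the time is missing. That section has no rule for an incomplete date. It otherwise follows the main method, "except that the NC=F and RM=F methods are not applied because they are not applicable to this endpoint".

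The principle to be implemented is in protocol sections 3 and 9.3.1 and SAP 6.3: whoever takes rescue is a failure at every assessment from then on (RM=F).

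**The concern.** An entry on the Rescue Medication CRF is evidence that rescue was taken. Under the definition above, a missing day or month cancels that evidence for efficacy, and less information about a known rescue gives a better outcome than more. If the rescue worked and the subject then reports no or mild pain, its benefit can be credited to study drug, which the composite strategy is meant to prevent.

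The endpoints mainly exposed are the sustained endpoints (steps 3 to 6 of the testing sequence), rescue use within 24 hours (step 15) and pain relapse (step 17). The sequence stops at the first non-significant result, so a borderline sustained endpoint decides whether later ones are formally tested. None of the co-primary sensitivity analyses varies rescue status: each applies RM=F first and only then handles missing pain or symptom data.

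**Working it through.** **Classification.** The rules applied to a subject with a single rescue record taken after dosing:

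| Rescue record | Endpoints under RM=F | Rescue use within 24 h (6.3.3.8) |
|---|---|---|
| Date and time complete | Failure at assessments at or after rescue | User if within 24 h |
| Date complete, time missing | Failure at assessments on or after that date | Excluded if dated no later than the day after dosing |
| Date incomplete | Rescue start missing: no RM=F failure | Kept, counted as non-user |
| No record | Rescue start missing: no RM=F failure | Kept, counted as non-user |

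The last two rows are identical, although one subject has a recorded rescue. The imputed rescue start in 7.1 does not help: it serves only the time-to-event analyses of 6.3.4.3 and fills in missing times, not dates.

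**What else a responder needs.** Sustained relief or freedom also requires the pain criterion at all assessed time points, non-missing scores at 2 and 24 hours (and 48 where relevant), and at most one missing score from 3 to 8 hours. Relapse counts any pain after 2 hours. So only a fraction of affected subjects becomes a false responder or non-relapser. The 24-hour rescue endpoint has no such filter.

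**Illustration, sustained endpoints.** The documents give neither a rescue rate nor a rate of incomplete dates, so every input here except n = 630 per arm (SAP 5) is an assumption. Let r be rescue use, u the share of users whose record is incompletely dated, and q the share of those who meet the pain criteria.

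- False responders per arm = 630 × r × u × q.
- With r = 25% (zavegepant) and 35% (placebo), u = 1% to 10% and q = 25% to 100%: from 630 × 0.25 × 0.01 × 0.25 = 0.4 to 630 × 0.25 × 0.10 × 1 = 15.8 on zavegepant, and from 0.6 to 22.1 on placebo.
- Bias in the difference = 100 × (0.25 − 0.35) × u × q = −0.025 to −1.0 points, against zavegepant.
- With r = 30% in both arms and equal u and q, the bias is 0.
- With r = 25%, u = 5% and q = 50% on zavegepant and u = 0 on placebo, it is 100 × 0.25 × 0.05 × 0.5 = +0.6 points, in favour of zavegepant.

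**Illustration, rescue use within 24 hours.** Assume the same 25% v 35%, all within 24 hours, so the true difference is −10.0 points. Take u = 10% in both arms.

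- As written: 0.9 × 25% = 22.5% v 0.9 × 35% = 31.5%, difference −9.0.
- Affected subjects excluded: 141.75/614.25 = 23.1% v 198.45/607.95 = 32.6%, difference −9.6.
- Counted as users: −10.0.

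At u = 1% the three differences are −9.9, −9.96 and −10.0.

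**Co-primary endpoints.** The stated power of 91%, 88% and 80% (joint) reproduces as 91.0%, 87.6% and 79.6% with a pooled two-proportion test, 630 per arm, two-sided alpha 0.05, and independence for the joint figure. At the planning rates, expected responders are 144 v 98 for pain freedom (p = 0.0010) and 266 v 212 for symptom freedom (p = 0.0017). For p to exceed 0.05, 20 zavegepant responders (20/630 = 3.2%) or 21 (3.3%), respectively, would have to become failures with none on placebo. Protocol 5.5 prohibits other headache medication in the first 2 hours, so that many incompletely dated early rescues in one arm is unlikely.

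**The case against.** Several points on the other side stand.

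- A reader might infer that known rescue users simply become responders. They do not, because the pain criteria still apply. Protocol 5.5 allows rescue for lack of relief at 2 hours or for return to moderate or severe pain, so many such subjects fail on the pain score anyway. What remains is mainly pain that returned and was treated between assessments, or rescue outside those conditions.
- The record is not lost. SAP 6.2.6.2 keeps Rescue CRF entries in the by-subject listing of non-study medications; what is lost is the RM=F failure. A further, fully dated rescue record restores the failure from its own date.
- Missing data do not always mean failure elsewhere. Sustained endpoints tolerate one missing score from 3 to 8 hours, relapse tolerates one after 2 hours, and 6.3.3.8 excludes rather than fails. The case rests on RM=F, not on a universal missing-equals-failure rule.
- Data queries may remove most partial dates. The protocol requires diaries to be returned and reviewed and source data verified. Whether the CRF accepts a partial date cannot be seen from these documents.

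A reader might also extend the point to subjects whose paper diary never came back. The documents do not carry that far: treating no record as no event is a usual convention for event logs, and neither document describes a diary-return variable.

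None of this answers the narrower point. When a rescue is recorded and its date remains incomplete, the rule as written misclassifies it.

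**Conclusion.** The point holds as a minor defect of derivation. The SAP states a rule that classifies a recorded rescue as no rescue, contrary to its own composite strategy and opposite in direction to its handling of a missing time.

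Its size cannot be fixed from the documents. Under the assumed ranges above, the effect on a sustained endpoint or on the 24-hour rescue difference is at most about 1 point, and zero for a sustained endpoint if both arms are equally affected. It would be tempting to size it from the prior study's 1,588 treated and 1,578 completing subjects. Completion measures neither diary return nor partial dates, so that figure is no guide.

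Nor do the documents support the inference that the rule favours zavegepant or inflates type I error. If placebo subjects rescue more and records are equally incomplete in both arms, it narrows the difference. Exposure of the co-primary endpoints is small, given the 2-hour prohibition and the margin at the planning rates.

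**What to change.** Before database lock:

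1. In SAP 6.2.6.2 and 7.1, state that after data queries a Rescue CRF record with an incomplete date counts as rescue from dosing for RM=F, unless its known date parts place it before dosing or after the assessment in question. Counting from dosing matches what 6.3 already does with an untimed record on the dosing day. Starting the count only after the 2-hour assessment would leave the inconsistency in place at 2 hours and earlier.
2. In 6.3.3.8, handle such a record like a missing time: exclude the subject in the main analysis, and add a sensitivity analysis counting the record as use.
3. Tabulate these records by arm. If diary return is recorded, tabulate non-return by arm as well.

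The cost is a few SAP sentences, one table and one extra run. The downside is some over-classification: a few subjects who rescued only after the endpoint period may be scored as failures, including at 2 hours. A subject whose record cannot be placed after the 2-hour assessment would also leave the relapse denominator, since that requires pain freedom at 2 hours as defined in 6.3.2.1. The tabulation shows whether either effect matters.
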